### 5.3 Protocol deviations

A summary table by cohort and overall with the number and percentage of subjects presenting deviations relating to inclusion/exclusion criteria (all eligibility criteria responses) will be prepared on the subjects included in the safety set. A summary table by cohort and overall with the number and percentage of subjects presenting other protocol deviations (all deviations judged relevant by the sponsor during the data-review meeting) will also be prepared. The corresponding listings will be provided with the status of deviation (minor/major, as assessed by the sponsor during the data-review meeting).

### 5.4 Definition of subgroups

The following subgroups will be considered to be investigated for efficacy; combinations of more than one subgroup may also be done. In case subgroup categories are smaller than 10 subjects within a cohort, subgroup categories might be combined.

- IL28B genotype (CC, CT, TT)
- HCV genotype/subtype (1a,1b, 1other, 2, 3)
- Prior treatment status (cirrhosis cohorts only) – prior pegylated interferon + ribavirin treatment with relapse

## 6. Demographic data and baseline characteristics

The analyses on demographic and other baseline characteristics will be performed on the safety set and PK set. Analyses on medical and surgical history, previous and concomitant medication, and compliance will be performed for the safety set.

Separate ad hoc summary tables of the demographic data and baseline characteristics for all subjects in cohorts 1b+4 (N=33) and cohort 5 (N=19) will be generated since, at the time of enrolment, all subjects in these two groupings were intended to dose for the same duration.

### 6.1 Demographic data

Subjects' demographic characteristics (age, sex, race, ethnicity, height, weight and BMI recorded at screening and Interleukin 28B genotype) will be summarised by cohort and overall, and listed.

### 6.2 Other baseline characteristics

HCV genotype as well as HCV RNA values at baseline (in IU/mL and  $\log_{10}$  IU/mL) will be summarised by cohort and overall, and listed.

Serology testing will be listed.

Positive results of serology will be listed.

Childbearing status (for female only) and contraception method will be listed.

Alcohol consumption will be listed.

Information related to liver biopsy and fibroscan will be listed as well as Child-Pugh class assessment and hepatocellular carcinoma assessment (only for compensated cirrhosis cohort). Fibroscan score and Child-Pugh score will be summarised by cohort and overall.

### **6.3 Medical and surgical history**

Information on medical and surgical history recorded at the screening visit will be coded according to the Medical Dictionary for Regulatory Activities (MedDRA®) Version 19.1.

A table with the number and percentage of subjects having at least one previous/ongoing medical and surgical history (except liver diseases) will be generated by cohort and overall. The same table will be provided for liver diseases (SOC: “Hepatobiliary disorders”). Previous/ongoing medical and surgical history (except liver diseases) and previous/ongoing medical and surgical history related to liver diseases will be listed separately.

### **6.4 Previous and concomitant medications**

Information on previous and concomitant medications will be coded according to the WHO drug Dictionary (WHO-DD) version of June 2015.

A previous medication will be defined as a medication stopped prior to the date and time of first administration of IMP. A concomitant medication will be defined as a medication which is taken by subjects any time during the treatment period (on or after the date and time of first IMP administration for each subject).

Incomplete dates (i.e. day and/or month and/or year missing):

- In case of a partial start date, the therapies are allocated to the phases using the available partial information, no imputation is done. If, for instance, for a therapy start date only month and year is available, these data are compared with the month and year info of the phases.
- In case of a completely missing start date, the therapy is considered as having started before the trial. In case of a completely missing end date, the therapy is considered as ongoing at the end of the trial.
- In case of a partial end date, the therapies are allocated to the phases using the available partial information, no imputation is done. If, for instance, for a therapy end date only month and year is available and are the same as month and year of the first IMP administration, the therapy is considered as concomitant.

A table with the number and percentage of subjects having at least one previous medication will be generated by cohort and overall (overall and by Anatomical Therapeutic Chemical (ATC) and by preferred name). A table with the number and percentage of subjects having taken at least one concomitant medication will be generated by cohort and overall (overall and by Anatomical Therapeutic Chemical (ATC) and by preferred name). Previous and concomitant medications will be listed separately.

### **6.5 Compliance**

A listing with IMP administration dates and times will be carried out for each study drug. Subjects that took additional doses (either extra doses on a dosing day (all drugs) or on

additional days other than those planned (for ODV QOD regimens) will be flagged in the listing. Time of meals intake will be listed as well.

## 7. Pharmacokinetic data

Two types of PK analysis will be performed for this study: 1) Non-compartmental analysis (NCA) for subjects participating in the PK substudy and 2) population PK in all subjects. This SAP will only cover the NCA PK analyses done in patients in the PK substudy. The population PK analysis will be described in a separate SAP and will have its own report.

The pharmacokinetic analysis will be performed on the pharmacokinetic set (PKS).

### 7.1 Generalities

The following rules for **PK parameters calculation** after each administration will be used:

Actual sampling times will be used for deriving PK parameters. In the case the actual sampling time will not be known, the scheduled time will be used, with appropriate footnoting. Actual sampling times will be checked for major aberrations. In case a major aberration occurs for an actual sampling time (i.e., >20.00% deviation from the scheduled time), this plasma concentration will be excluded from descriptive statistics in the plasma concentration table and reported in the CSR.

If an entire concentration-time profile is below the limit of quantification (BLQ), the profile will be excluded from the PK analysis.

All BLQ values will be replaced by “0”.

All embedded BLQ values (BLQ value between two measurable concentrations) will be treated as missing. Details of this exclusion must be documented in the clinical study report.

For the determination of  $\lambda_z$ , only those data points judged to describe the terminal log-linear decline resulting in an adjusted coefficient of determination value > 0.9 will be used in the regression. A minimum of 3 data points will be used in calculating  $\lambda_z$  (excluding  $C_{max}$ ). The number of points and the lower and upper limits of the terminal phase will be identified in the study data and in the CSR.

If there are late positive concentration values following 2 BLQ concentration values in the apparent terminal phase, these values will be evaluated. If these values are considered to be anomalous or to introduce a substantial bias, they will be set to missing and excluded from the PK analysis.

The following rules for **plasma concentration versus time graphic representation** will be used:

No graphic representation will be made if all values are BLQ.

All BLQ values will be replaced by “0”.

All BLQ values will not be shown on semi-logarithmic plots.

Profiles and individuals values considered to be outliers should be included in the individual plots and excluded in the mean plots.

Actual sampling times will be used for individual subjects PK profiles and nominal sampling times should be used for mean plots.

All subjects will be plotted with the same scale and range of values on the x- and y-axes

The following rules for **mean plasma concentration calculation** will be used:

If more than half (>50%) of the values at a single time point are BQL, mean and median values will be reported as BQL. Standard deviation and %CV will not be reported; maximum and minimum values will be reported as observed (including BQL).

If more than (or equal) half of values are not BLQ: statistics will be calculated considering BLQ values as zero.

**For summary statistics for PK parameters:**

If more than (or equal to) half of values are available: statistics will be calculated considering available values.

If less than half of values are present: mean will not be calculated and presented as missing. Min, median and max value on available values will be presented.

All concentrations below the limit of quantification or missing data will be labelled as such in the concentration data listings.

## **7.2 Plasma pharmacokinetic concentrations and parameters**

### **7.2.1 Plasma pharmacokinetic parameters**

Blood samples will be drawn for AL-335, SMV and ODV (depending on the cohorts) on:

- On Day 1 at 0 hour,
- On Week 2 at 0, 0.5, 1, 2, 3, 4, 6, 9, 12 and 24 hours (For PK substudy only),
- On Week 3 at 0, 2-4 hours,
- On Week 4 at 0, 6-8 hours,
- On Week 6 at 0, 2-4 hours,
- On Week 8 at 0, 6-8 hours (8 or 12 Week Cohorts),
- On Week 10 at 0, 2-4 hours (12 Week Cohorts),
- On Week 12 at 0, 6-8 hours (12 Week Cohorts).

For subjects in the PK substudy, relevant plasma pharmacokinetic (PK) parameters will be calculated for AL-335 and its metabolites (ALS-022399 and ALS-022227), SMV and ODV by standard non-compartmental methods for those subjects with sufficient plasma concentration data. The rules defined in the previous [section 7.1](#) will be used.

The different areas under the concentration-time curve (AUC) will be calculated using the linear Trapezoidal summation (both ascending and descending phase).

The following plasma pharmacokinetic parameters will be calculated for AL-335 and its metabolites (ALS-022399 and ALS-022227), SMV and ODV:

Parameters (unit)	Definition
$C_{\min}$ (unit)	Minimum observed plasma concentration
$C_{\max}$ (unit)	Maximum observed plasma concentration
$C_{\text{trough}}$ (unit)	Concentration at the end of a dosing interval before the next dose administration (Pre-dose or $C_{0h}$ )
$t_{\max}$ (h)	Time to reach maximum plasma concentration
$AUC_{0-\text{last}}$ (unit.h)	
Area under the plasma concentration-time curve from time zero to last measurable (Non-BLQ) plasma concentration
 
In cases where a subject's <math>AUC_{0-\text{last}}</math> is estimated over a time interval that is very different from that of the other subjects in the group, it is recommended that subject's <math>AUC_{0-\text{last}}</math> could be excluded from the calculation of descriptive statistics. All exclusions must be clearly documented in the CSR.
 
In cases where more than half of subjects have a different <math>t_{\text{last}}</math>, it may not be appropriate for the descriptive statistics for <math>AUC_{0-\text{last}}</math> to be reported.

$AUC_{0-24}$ (unit.h)	Area under the plasma concentration-time curve from time zero to 24 hours
$AUC_{0-48}$ (unit.h)	Area under the plasma concentration-time curve from time zero to 48 hours (only for ODV and QOD cohorts)
$C_{\text{ss,avg}}$	
Average concentration of the drug calculated as follows:
 $C_{\text{ss,avg}} = AUC_{0-\tau} / \tau$
$C_{\text{last}}$ (unit)	Last observed plasma concentration
$t_{\text{last}}$ (h)	Time to reach last plasma concentration

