6.0 STUDY PROCEDURES

6.1 Schedule of Events

Table 6-1. Schedule of Events for 8 or 12*-Week Treatment Groups

Assessments	Interval	Day			Week**							
	Screen -50 to -1	1	2	3	1	2	3	4	5	6	7	8
AL-335+ODV±SMV ¹		<----->										
Obtain informed consent before study procedures	X											
Demographics	X											
Height, Weight, BMI ²	X											X ²
Drug Screen	X											
Medical History	X											
Echocardiogram	X							X (±3 days)				X (±3 days)
Triplicate 12-Lead electrocardiogram	X	X			X	X	X	X	X	X	X	X
Physical Exam and vital signs ³	X	X			X	X	X	X	X	X	X	X
Hepatitis and HIV screen (HBsAg, HBsAB, HBcAb, HCVAb, HIVAb)	X											
Alpha-fetoprotein, glycosylated HbA1C	X											
Liver Ultrasound (subjects with cirrhosis)	X											
HCV genotype	X											
IL28B genotype		X										
Enrollment⁴		X										
AE & Conmed Evaluation	X	X	X	X	X	X	X	X	X	X	X	X

¹ Cohorts 1b, 2 to 16 may or may not include SMV. Dosing frequency will be qd except possibly for ODV which may also be dosed qod.

² Weight only collected at last treatment visit.

³ Complete Physical Exams, including vital signs (BP, HR, RR, body temperature), are to be done at screening, predose on Day 1, early termination, safety follow-up visits. Symptom directed physical exams and vitals are to be collected as necessary at all other visits.

⁴ Enrollment may take place up to 4 days before first dose.

Table 6-1. Schedule of Events for 8 or 12*-Week Treatment Groups

Assessments	Interval	Day			Week**							
	Screen -50 to -1	1	2	3	1	2	3	4	5	6	7	8
PK Samples ⁵		X				X	X	X		X		X
Hematology ⁶	X	X			X	X		X		X		X
Serum Chemistries ⁶	X	X			X	X		X		X		X
Urinalysis	X	X			X	X		X		X		X
ALT/AST ⁶	X	X			X	X	X	X	X	X	X	X
HCV RNA concentrations ⁷	X	X	X	X	X	X	X	X	X	X	X	X
Plasma for drug resistance monitoring ⁸		X	X	X	X	X	X	X	X	X	X	X
Pregnancy Test ⁹	X							X				X
Optional stored serum sample ¹⁰	X	X			X	X	X	X	X	X	X	X

⁵ A single predose PK sample will be collected at each indicated visit for AL-335 (and metabolites), ODV and SMV concentrations for all subjects. In addition, PK samples will be collected at Weeks 3 and 6, 2-4 hours postdose, and at Weeks 4 and 8, 6-8 hours postdose. Subjects in the intensive PK subset will have the following samples collected at the Week 2 visit Predose (within 0.5 hour) and 0.5, 1, 2, 3, 4, 6, 9, and 24 hours postdose.

⁶ Blood for routine safety evaluations should be collected in a fasted state.

⁷ Plasma for HCV RNA analysis to be collected predose at Day 1.

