### 7.2.2 Plasma pharmacokinetic analysis

Listings with plasma concentrations of AL-335, ALS-022399 and ALS-022227, SMV and ODV (including PK blood sampling dates and times) and PK parameters will be provided by cohort, dose, and subject. These listings will be performed on all subjects with an available profile (complete or incomplete), including those who are excluded from the PKS.

A specific listing will be also done focussing on subjects who either discontinue the study for an adverse event, experience a severe adverse event or a serious adverse event.

Individual plasma concentrations for all subjects and PK parameters of AL-335, ALS-022399 and ALS-022227, SMV and ODV including descriptive statistics for subjects participating in the PK substudy will be presented in tables by cohort and by pooled cohorts.

Graphs for plasma concentration versus time profiles of AL-335, ALS-022399 and ALS-022227, SMV and ODV will be generated on linear and log/linear coordinates for arithmetic mean ( $\pm$ SD) by cohorts.

In addition, the plasma concentration versus time profiles of AL-335, ALS-022399 and ALS-022227 will also be presented on the same graph or as a separate graph on linear and log/linear coordinates for arithmetic mean ( $\pm$ SD) by pooled cohort.

Moreover, the plasma concentration versus time profiles of AL-335, ALS-022399 and ALS-022227, SMV and ACH-3102 will be presented graphically on linear and log/linear coordinates for each subject.

Pre-dose (“trough”) concentrations of AL-335, ALS-022399 and ALS-022227, SMV and ODV for all subjects at all available timepoints will be presented graphically on linear coordinates for arithmetic mean ( $\pm$ SD) by cohorts and by pooled cohorts.

Scatter plots will be generated for the comparison of  $C_{\text{trough}}$ ,  $C_{\text{max}}$ , and  $AUC_{0-\tau}$  parameters of AL-335, ALS-022399, ALS-022227, SMV and ODV by cohorts and by pooled cohorts.

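### In the QOD cohorts ODV AUC0-48 and Css,avg have neither samples nor a rule beyond 24 h, and plotting AUC0-tau across QOD and QD cohorts misleads by a factor of two

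*SAP*

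**What the plan says.** SAP 3.1 gives ODV as 50 mg QD in Cohort 1, 50 mg QOD in Cohorts 1b to 6, and 25 mg QD in Cohorts 7 to 12.

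SAP 7.2.1 lists, among other parameters, AUC0-24, the ODV "Area under the plasma concentration-time curve from time zero to 48 hours (only for ODV and QOD cohorts"), and Css,avg defined as AUC0-tau over tau. Parameters are derived "by standard non-compartmental methods for those subjects with sufficient plasma concentration data", and AUCs "will be calculated using the linear Trapezoidal summation (both ascending and descending phase"). Ctrough is the concentration at the end of a dosing interval and is identified with the predose value.

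The intensive samples are taken "On Week 2 at 0, 0.5, 1, 2, 3, 4, 6, 9, 12 and 24 hours (For PK substudy only"); the next PK sample is at Week 3. Protocol Tables 6-1 to 6-3 give "Predose (within 0.5 hour) and 0.5, 1, 2, 3, 4, 6, 9, and 24 hours postdose", which has the same end point but no 12 h sample. Neither SAP 7.1 nor 7.2.1 says how 24 to 48 h is to be filled.

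SAP 7.2.2 states: "Scatter plots will be generated for the comparison of" Ctrough, Cmax and AUC0-tau, by cohort and by pooled cohort. SAP Appendix 3 lists the ODV scatter and box plots of Cmax and AUC0-tau by cohort (outputs 14.2.2.3.2 and 14.2.2.3.3). The SAP abbreviation list defines AUC0-tau as the AUC over one dosing interval. SAP 7.2.2 also plots mean predose concentrations at all available time points.

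**The concern.** Half of the QOD dosing interval has no samples, yet two listed parameters need it. Without a stated rule, a programmer may extrapolate, impute, divide AUC0-24 by 24 or by 48, or leave the parameter blank. These choices give materially different answers.

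The comparison metric has a separate defect. AUC0-tau covers 48 h in one set of cohorts and 24 h in the other, so a plot by cohort mixes window length with exposure. The contrast most affected is Cohort 6 against Cohorts 7 to 12: subjects with cirrhosis, the same mean daily ODV dose, and two different schedules. Exposure matters for this drug because Protocol 1.3 names the heart as a target organ of ODV toxicity, and Protocol 5.7 caps projected exposures at the nonclinical no-adverse-effect level.

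The predose plots raise a related question. Under QOD dosing a predose ODV sample can be 24 h or 48 h after the last ODV dose, and nothing in the SAP separates the two.

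**Working it through.** **1. The plan's own PK figure.** Protocol 9.3 gives n = 20, SD 0.77 on log AUC0-24h and 90% confidence. With t(0.95, 19 df) = 1.729: exp(±1.729 × 0.77/√20) = exp(±0.298) = 74.25% to 134.68%. The stated values are 74.2% and 134.8%, so the figure is reproduced to rounding. It concerns AUC0-24h; no precision is stated for AUC0-48.

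**2. AUC0-tau across schedules.** At steady state with linear kinetics, AUC0-tau = F × Dose/CL and Css,avg = AUC0-tau/tau.
- 50 mg QOD against 25 mg QD: AUC0-tau ratio 50/25 = 2.00; Css,avg ratio (50/48)/(25/24) = 1.00.
- 50 mg QD against 50 mg QOD: AUC0-tau ratio 50/50 = 1.00; Css,avg ratio (50/24)/(50/48) = 2.00.

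Allowing for incomplete steady state at Week 2 (half-lives up to 200 h), the AUC0-tau ratios become 2.00 to 2.06 and 0.97 to 1.00. For context, Protocol Table 1-2 gives mean ODV AUC0-24h of 11,809 in Cohort 1 and 5,407, 4,416 and 7,087 ng·h/mL in Cohorts 1b, 2 and 3. The ratios are 2.18, 2.67 and 1.67, from small samples (N = 11, 8, 3 and 6).

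**3. What lies beyond 24 h.** The documents give no ODV half-life, so a range is assumed. The check uses a one-compartment model with Tmax 6 h (the usual median in Table 1-2), superposed to steady state at 50 mg QOD. The last column sets C48 = C0 (same-profile predose), so that AUC0-48 = AUC0-24 + 12 × (C24 + C0).

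| Assumed half-life (h) | AUC0-24 / AUC0-48 | AUC0-24 / mean daily AUC | C48 = C0 result / true AUC0-48 (SAP times; protocol times) |
|---|---|---|---|
| 12 | 0.76 | 1.52 | 1.043; 1.048 |
| 24 | 0.65 | 1.29 | 1.015; 1.017 |
| 48 | 0.58 | 1.15 | 1.004; 1.005 |
| 100 | 0.54 | 1.07 | 1.001; 1.001 |
| 200 | 0.52 | 1.04 | 1.000; 1.000 |

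Using AUC0-24/24 as Css,avg therefore overstates it by 4% to 52%, and using AUC0-24/48 understates it by 24% to 48%. The C48 = C0 route stays within about 5%; with eight QOD doses instead of full steady state, its lowest ratio is 0.985, at 200 h.

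A rough guide to where ODV lies: Protocol 1.2.1.2 gives Cohort 1 mean Cmax 636 and C24h 384 ng/mL. With Tmax at 6 h, the apparent half-life is 18 × ln 2 / ln(636/384) = 24.7 h.

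**4. Dosing phase.** If QOD dosing starts on Day 1, ODV days are odd. The SAP target days for Weeks 2, 3, 4, 6 and 8 are 14, 21, 28, 42 and 56, of which only 21 is odd. Day 14, the profile day, would then be an off-day, with its predose sample 24 h after the last ODV dose. The documents do not state the phase, and the ±1 day visit window can reverse it.

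**5. The 12 h sample.** Protocol Appendices C to E allot 6 mL for the single Day 1 sample, 12 mL for the two samples at Week 3, and 60 mL at Week 2. At 6 mL each that is ten samples, which fits the SAP list; the protocol footnote lists nine (54 mL).

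**The case against.** The strongest reply is that one sentence is missing, not a method. The SAP already equates end-of-interval and predose concentration, restricts noncompartmental analysis to adequate data, and lists Css,avg, which corrects for tau. Its PK pooling never mixes QOD with QD. Population PK in all subjects will estimate AUCtau under a separate plan (Protocol 10.5, SAP 7). The affected outputs are descriptive plots with no hypothesis test. All of this stands, and it limits the seriousness. It does not supply the 24 to 48 h rule, and Css,avg is not what is plotted.

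Stronger readings are tempting but not supported:
- **AUC0-48 is impossible to obtain.** Not so: the C48 = C0 route needs no new sample.
- **Terminal-slope extrapolation fails under the SAP's own rule** ("A minimum of 3 data points will be used in calculating" the slope, excluding Cmax). The SAP does not assign that method to AUC0-48, and on its schedule a Tmax of 6 h leaves 9, 12 and 24 h.
- **The 12 h sample is not taken.** The blood volumes, and ODV Tmax ranges reaching 12 h in Cohorts 1 and 1b, suggest that it was.
- **AUC0-tau always inflates QOD exposure.** Against Cohort 1 it hides a difference instead.
- **Mean trough plots will zigzag.** This depends on the unstated phase and the visit window. The ODV Tmax ranges in Table 1-2 for the QOD cohorts (3 h at the earliest) look like dosing-day profiles, although no rule requires that.
- **QOD AUC0-tau feeds the cardiac margin.** Protocol 1.3.1 states that margin against 25 mg QD exposure, and nothing links the two.

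**Conclusion.** The point holds in this form. For ODV in Cohorts 1b to 6, AUC0-48 and hence Css,avg rest on an interval with no observed data after 24 h and no pre-specified rule. The unobserved part is 24% to 48% of AUC0-48 for assumed half-lives of 12 to 200 h, and about 35% at 24 h. The planned AUC0-tau plots mislead in both directions: about two-fold too high for 50 mg QOD against 25 mg QD at equal average concentration, and no visible difference against 50 mg QD where average concentration differs two-fold. Some predose ODV values in QOD cohorts may not be end-of-interval troughs.

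The two-fold result assumes linear kinetics and approximate steady state, but no particular half-life. The percentages rest on the assumed half-life range and a one-compartment shape with Tmax 6 h. This is a descriptive secondary analysis, so the change is worth making before the PK outputs are programmed but does not threaten the trial's primary objective.

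**What to change.** 1. **State a 24 to 48 h rule.** Where the dosing record shows that the profile began with an ODV dose taken about 48 h after the previous one, set C48 to the same-profile predose concentration, with steady state assumed and checked. Compute AUC0-48 as AUC0-24 plus the 24 to 48 h trapezoid. Otherwise report it as not estimable, or take it from the population PK model.
2. **Compare QOD and QD cohorts on Css,avg** (AUC0-tau/tau), and label tau on any AUC0-tau plot that is kept.
3. **Classify QOD predose ODV samples by actual time since the last ODV dose**, and summarise as trough only those at about 48 h.
4. **Reconcile the 12 h sample** between SAP 7.2.1 and Protocol Tables 6-1 to 6-3.

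The cost is SAP wording and PK programming; no new samples are needed. The downside is reliance on approximate steady state at Week 2, and some profiles may turn out not estimable, particularly if the visit fell on an ODV off-day.
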